##### 2. Pre-Test Counseling, Visit 1 (Remote Telegenetics Arms A and B)

Those who contact the Penn Telegenetics will be registered with the Penn Telegenetics Program, consistent with routine clinical care. They will be scheduled with a Penn Telegenetics Genetic Counselor according to their study arm. Participants in Arms A and B will be asked to complete a study survey following their pre-test counseling sessions, Visit 1 (T1) (**Appendix F**).

**ARM A: Remote telegenetic counseling by videoconference:** Those who contact Penn Telegenetics in Arm A will complete their pre-test counseling session (Visit 1) by videoconference, utilizing communication protocols and checklists adapted from related studies

**(Appendix G)** (50). Penn GCs are licensed in all U.S. states that require licensure to provide remote telegenetic services (49). Consistent with standard clinical practice, GCs will review personal and FH, the risks, benefits and limitations of genetic testing, testing options based on their personal and FH (e.g. *TP53* testing or a panel of cancer susceptibility genes) and the costs associated with genetic testing. If the participant consents, this session will be recorded for research and training purposes.

**Videoconferencing Technology platforms:** Participants will be provided links to download secure, HIPAA compliant, videoconferencing software on their home computer or device. The Penn Telegenetics team provides back-up systems if one platform is not able to launch or fails to maintain connectivity. In our communication protocols, if videoconference technology fails, GCs will convert the session to phone.

**ARM B: Remote telegenetic counseling by phone:** Participants will complete their pre-test counseling (Visit 1) session by phone with a Penn Telegenetic Counselor (GC) utilizing communication protocols and checklists adapted from related studies (Appendix G) (48). The remainder of procedures for pre-test counseling are as described above for Arm A. If the participant consents, this session will be recorded for research and training purposes.

**ARM C: Usual Care Arm:** Participants in the usual care arm will receive usual care services depending on which referral method they choose and if they initiate services. As below, after the 6-Month Outcome Survey, if they have not had genetic services through usual care they will be offered services and re-randomized to Arm A/B in a waitlist design.

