#### 5. Completion of Primary Outcome 6-Month Status Survey (Usual Care Arm & Certain Remote Telegenetics Arms Participants, **Appendix I1**)

Participants on the usual care arm will be contacted at the 6-month timepoint (6-months post randomization) to assess uptake of genetic services. Participants on Arms A and B that have not completed genetic counseling or testing will also be contacted at the 6-month timepoint to assess uptake of genetic services through the 6-Month Status Survey. Those who have had genetic testing will be asked to provide authorization for the study team to obtain a copy of their genetic test result for the purpose of research (**Appendix I2**).

Participants on Arm C that have not had genetic testing at 6 months will be offered telegenetic services (waitlist design, see **Study Schema**). This option will not be shared at enrollment. Rather, they will be told that after they complete the 6-Month Status Survey, we will review again genetic testing options with them.

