### 3.6 Number of experimental subjects

An approximate 520 participants are anticipated to enroll to meet enrollment goals for the randomized trial (both Aims 1 and 2). As outlined above, once enrollment goals for Aim 1 are reached (120 completed baseline survey and sent randomization flyer), we will halt enrollment of Arm C. We will continue to enroll to Arms A and B to meet enrollment goals for Aim 2.

An approximate 15-30 patients, 15-30 primary providers and 15-30 primary care provider office staff participants are anticipated to enroll for aim 3, for a total of up to 90 additional participants (**Appendix K**).

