**Sample Size Justification for Aim 2:** We further chose our sample size such that we would have sufficient power for Aim 2 comparisons of the videoconference versus phone arms. After rerandomization of the waitlist group, we anticipate potentially having 180 people/arm randomized to the videoconference or phone arms. Based on prior experience, we anticipate that loss to follow-up will be less than 28% in each arm, leaving us with 130 evaluable participants with follow-up data in each group ( $180 - 180 \times 0.28 = \text{approximately } 130$ ). Some of the loss to follow-up will occur prior to the waitlist group being rerandomized. We used our pilot data to determine power for this aim (see Table 2 for estimates). We assumed 85% power and a 1.67% Type I error rate. We used a 1.67% Type 1 error rate (2-sided) by applying a Bonferroni correction for the three outcomes of interest to the typical 5% Type I error rate ( $5\% / 3 = 1.67\%$ ). We see in Table 2 that we have excellent power for all three arms with at least 95/arm, which is well below our expected 130/arm anticipated sample size. Table 2 also demonstrates that we have sufficient power for subgroup analyses, with a sample size of just 22/arm needed for knowledge comparisons between arms.

Table 2. Sample size calculations for Aim 2		
Variable	Change scores + (SD) of phone vs. videoconferencing	Number needed*
Knowledge	+5.7 (11.2) vs. +18.6 (12.6)	22/arm
Cancer specific distress**	+3.6 (12.4) v. -2.6 (12.3)	95/arm
Depression	-0.2 (2.0) vs. -1.6 (2.0)	50/arm

+Baseline to post genetic testing \*85% Power, 1.67% alpha; \*\*intrusive subscale

Amendment note added June 5, 2023: Our anticipated visit 2 completion sample size for the phone and videoconferencing arms will be 60 to 80 per arm, which is below are initial goal of 180/arm. With 60 to 80 per arm, we will still have adequate power for the knowledge and depression endpoints.

Analyses for Aim 3 included in **Appendix K**.

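### The Aim 2 sample sizes do not reconcile: 520 enrolled implies about 250 per arm rather than 180, the 130 evaluable leaves out testing uptake, and 60–80 completers are set against the wrong planned figure

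*Combined protocol and SAP*

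**What the plan says.** **Total.** Section 3.6: "An approximate 520 participants are anticipated to enroll to meet enrollment goals for the randomized trial (both Aims 1 and 2"). Section 2.0 also describes a three-arm randomised study in 520 survivors. Sections 3.3 (Randomization) and 3.6 close Arm C once 120 people have completed the baseline survey and been sent the flyer, and keep Arms A and B open for Aim 2.

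**Aim 2 size.** Section 4.0 (Sample Size Justification for Aim 2), counting after the waitlist group has been re-randomised: "we anticipate potentially having 180 people/arm randomized to the videoconference or phone arms". It then takes off losses to reach the analysed count, "leaving us with 130 evaluable participants with follow-up data in each group", and adds "Some of the loss to follow-up will occur prior to the waitlist group being rerandomized". The loss assumed is less than 28% per arm. From Table 2 it concludes that power is excellent throughout, because the largest requirement, 95 per arm, lies well under the 130 expected.

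**June 2023 note.** Added at the end of the same section, it lowers the expected number completing visit 2 to 60–80 per arm, "which is below are initial goal of 180/arm", and says power remains adequate for knowledge and depression. The Schema footnote adds that the 60–80 includes waitlist participants from Arm C.

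**Endpoint.** Section 4.0 (Analyses for Aim 2) defines the primary change scores from baseline to just after genetic testing. Section 3.3 places that survey (T2) after result disclosure.

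**Waitlist.** Section 3.3, items 2 and 3, on Arm C after six months: "if they have not had genetic services through usual care they will be offered services and re-randomized to Arm A/B in a waitlist design". Item 5 of the same section: "Participants on Arm C that have not had genetic testing at 6 months will be offered telegenetic services".

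**The concern.** Three links in the chain from enrolment to analysed participants do not fit together. The enrolment total and the Arm C cap give more people in Arms A and B than Section 4.0 says will be randomised. The step from randomised to evaluable allows for loss to follow-up but not for people who are never tested and so never have a T2 survey. The 2023 note then measures completers against a count of people randomised.

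Arms A and B stay open until the Aim 2 goals are met, so a reader needs to know what those goals are. The figures also decide whether distress, one of three primary Aim 2a outcomes, was ever expected to reach its stated size, and how large the later shortfall is. The waitlist criterion decides who from Arm C enters the Aim 2 comparison.

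**Working it through.** **1. The plan's own figures reproduce.**
- Evaluable per arm: 180 × (1 − 0.28) = 129.6, about 130.
- Table 2, two-sided alpha 0.05/3, 85% power, t-test, pooled SD = √((SD₁² + SD₂²)/2):

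| Outcome | Difference | Pooled SD | Computed n per arm | Stated |
|---|---|---|---|---|
| Knowledge | 12.9 | 11.92 | 21.6, so 22 | 22 |
| Distress | 6.2 | 12.35 | 94.8, so 95 | 95 |
| Depression | 1.4 | 2.0 | 49.5, so 50 | 50 |

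**2. From 520 to randomised per arm.** Inputs: 520 (Sections 2.0 and 3.6), Arm C 120 (Sections 3.3 and 3.6), usual-care testing uptake 17% (Section 4.0, Aim 1).
- Before the waitlist: (520 − 120)/2 = 200 per arm.
- Re-randomised from Arm C at 17% uptake, no other loss: 120 × 0.83 = 99.6.
- With the waitlist: (400 + 99.6)/2 = 249.8, about 250 per arm.
- Range: Section 1.0 gives 6% counselling and 17% testing under usual care, so uptake of either is at most 23%. Uptake of 23% gives (400 + 92.4)/2 = 246; 6% gives (400 + 112.8)/2 = 256; zero gives 260.
- If 28% of Arm C is also lost before re-randomisation: 120 × 0.83 × 0.72 = 71.7, and (400 + 71.7)/2 = 236 per arm.
- In reverse, 180 per arm at 17% uptake needs 360 − 99.6 = 260 people in Arms A and B, or about 380 enrolled with Arm C. That is not 520.

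**3. From randomised to evaluable.** Inputs: testing rates of 53% (29/55, Section 4.0) and 61% (Section 1.0), both from the earlier trial of remote services delivered on site in community practices.
- Tested among 180: 180 × 0.53 = 95; 180 × 0.61 = 110, before any survey loss.
- An evaluable count of 130 would need 130/180 = 72% tested with no loss at all.
- If the 28% loss applies among those tested: 95.4 × 0.72 = 69; 109.8 × 0.72 = 79.
- The same steps from 250 per arm: 250 × 0.53 × 0.72 = 95; 250 × 0.61 × 0.72 = 110. Distress needs 95, so the choice of starting figure settles whether its planned size was in reach.

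**4. The comparison in the 2023 note.**
- Against 130 evaluable: 1 − 80/130 = 38%; 1 − 60/130 = 54%.
- Against 180 randomised, as the note has it: 1 − 80/180 = 56%; 1 − 60/180 = 67%.

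**5. Power at the amended size** (t-test, two-sided alpha 0.05/3, Table 2 effects):

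| Outcome | 60 per arm | 80 per arm |
|---|---|---|
| Knowledge | >99.9% | >99.9% |
| Depression | 92% | 98% |
| Distress | 63% | 77% |

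**6. Waitlist criteria.** Items 2 and 3 of Section 3.3 exclude anyone who has had genetic services; item 5 excludes only those who have been tested. The rules differ for people counselled but not tested. At 6% counselling, with none of those people tested, that is at most 120 × 0.06 = 7 people.

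**The case against.** **The 180 is hedged.** Section 4.0 says this number is potential and that some loss precedes re-randomisation, so 180 is best read as an upper bound. That is fair, but it does not reconcile the figures: 520 gives 200 per arm before anyone from the waitlist is added, already above that bound.

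**520 may be an inflated count or a count of consents.** Taking 28% loss off a complete-data total of 360 would need 360/0.72 = 500 enrolled, which is near 520. But the 120 cap on Arm C is counted at baseline survey and flyer, and Section 4.0 takes 28% off the 180 in any case. Reading 520 as consents before eligibility screening sits badly with Section 2.0, which calls it the size of the randomised study. It is also true that 250 × 0.72 = 180, so 180 could have been a completer goal under 520; the text, however, defines 180 as randomised.

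**A stronger reading is tempting.** Because (240 + 120)/2 = 180, a reader might infer that 180 per arm requires every Arm C participant to be re-randomised, that total enrolment is really 360, and that 160 people are unaccounted for. The documents do not support this. The plan never writes that sum; the 240 is a complete-data figure; Arms A and B go on enrolling after Arm C closes; and at 520 no Arm C participant is needed to reach 180. No section gives 360 as total enrolment.

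**The note already corrects the expectation.** In part it does. The 60–80 agrees with the Schema footnote and lies close to the 69–79 derived above, and the claim for knowledge and depression is right, since 22 and 50 are both below 60. But the note leaves distress unmentioned, and the statements about 130 per arm and excellent power remain in the current text. The Schema figure was not readable, so a fuller participant flow may be shown there; the point concerns the readable text.

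**Conclusion.** The concern holds as a failure of the stated Aim 2 sizes to reconcile. With 520 enrolled and Arm C capped at 120, the plan implies 200 per arm before the waitlist and about 250 with it, not 180; the 250 assumes 17% usual-care uptake and no other loss. The 130 evaluable was not attainable from 180 per arm at the testing rates the plan cites, even with no survey loss; those rates come from a different setting, and the 69–79 further assumes that the 28% applies among those tested. The 2023 shortfall is 38–54% against the matching figure of 130.

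The practical consequence is confined to distress, whose power falls to about 63–77%, so the claim of excellent power for all three outcomes no longer holds. That sentence literally refers to three arms; Table 2 lists three outcomes, and I read it that way. The difference between the waitlist criteria is real but small.

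**What to change.** Restate one participant flow in Section 4.0 and carry it into Sections 2.0 and 3.6: total enrolled, randomised per arm, re-randomised from Arm C, tested, and visit 2 completers per arm, with the assumed uptake and loss at each step. Make 520 and 180 per arm consistent with it. In the 2023 note, set 60–80 against 130 rather than 180. Withdraw or restate the sentences on 130 per arm and on excellent power for all three outcomes, and give the power for distress at 60–80. Reconcile items 2, 3 and 5 of Section 3.3 to a single waitlist criterion; which one is for the investigators to decide.

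The cost is protocol wording and one table. No added enrolment is proposed. The stated position for Aim 2 becomes less favourable, chiefly for distress.

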**Sample Size Justification for Aim 1:** We chose our sample size to have sufficient power for both Aims 1 and 2. For Aim 1, the sample size was selected to detect average differences in the primary endpoint (a composite variable indicating either genetic testing or genetic counseling) between the primary randomization arms of interest. The primary comparison groups will be the usual care/waitlist group versus the combined remote telegenetics groups (phone or video conference as one group); the primary analysis will consider the groups prior to the waitlist rerandomization. Preliminary data demonstrated that uptake of genetic testing from an ongoing registered randomized trial of remote telegenetic services vs. usual care for cancer genetic testing in community practices was at least 53% (29/55 with uptake) in the intervention arm, but only 17% (4/24 with uptake) in the control arm. With 120 patients in the usual care/waitlist group and 240 patients in the combined telegenetics groups with complete data (after accounting for loss to follow up), we will have  $>99\%$  power to detect a similar difference in uptake of genetic testing. This assumes a 1% Type I error rate (2-sided) and the use of Fisher's Exact Test. We set the Type I error rate to a conservative 1% to partially account for multiple hypothesis testing when including secondary outcomes and potential moderators in Aim 3. Given the magnitude of the pilot data differences, we anticipate excellent power for the moderator/subgroup analyses. The comparison of the usual care/waitlist group to the combined telegenetics group will be the comparison used to determine if the study accomplishes its primary objective. The uptake of pre-test counseling (Aim 1 secondary objective) and comparison between the phone and videoconference groups (see Aim 2a) are secondary objectives.

**Analyses for Aim 2:** *We hypothesize that remote telegenetic services by videoconferencing will be associated with greater decreases in cancer related distress and depression and increases in knowledge when compared to phone services.* Our primary outcomes for Aim 2a include changes in 1) cancer related distress; 2) depression; and 3) knowledge. We will compare the usual care at baseline group to the combined arms receiving remote services at baseline. For

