comparisons between the remote videoconferencing versus phone groups, we will assign participants to the remote group assigned at baseline, or after rerandomization for the waitlist group. Our primary change scores for the first three variables will be change between baseline and immediately post genetic testing. For the waitlist group, there will be a second baseline measurement after the usual care period has ended. For the 3 primary analyses in Aim 2, we will use T-tests. We will assess balance of potential confounders (e.g. age, race, study site, waitlist assignment) between arms using T-tests or Fisher's exact tests as appropriate. Waitlist group will be considered a confounder in these secondary regression analyses. We will use multiple linear regression models to control for potential confounders inadequately balanced. We will include in the models the confounding variables and indicator (binary 0/1 variables) to indicate randomization arms (leaving one group out as the reference). For longitudinal analyses, we will examine time trajectories using regressions estimated by Generalized Estimating Equations (GEE) to account for within subject temporal correlation. Panel time will be included via indicator variables. We will also include interaction terms between randomization arm and time indicators to investigate temporal effects.(82) We will repeat analyses, but assign participants to per-protocol (i.e. restricting sample to those who properly used the assigned method of disclosure) or as-treated groups (e.g. assigning all participants to a group based on the method of disclosure used, regardless of assignment). For Aim 2 secondary outcomes, we will use multiple linear regressions for continuous outcomes and multiple logistic regressions for binary outcomes using GEE-estimation as described.

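### Holm's step-down rule would raise power for the Aim 2a distress outcome by up to 11 to 15 points over single-step Bonferroni, at the same 5% familywise error

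*Combined protocol and SAP*

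**What the plan says.** All of this is in section 4.0 of the combined protocol and SAP.

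- **Outcomes** (Analyses for Aim 2): "Our primary outcomes for Aim 2a include changes in 1) cancer related distress; 2) depression; and 3) knowledge".
- **Test** (Analyses for Aim 2): "For the 3 primary analyses in Aim 2, we will use T-tests". No significance level or multiplicity rule is given there.
- **Error rate** (Sample Size Justification for Aim 2): "We assumed 85% power and a 1.67% Type I error rate". The level is explained as follows: "We used a 1.67% Type 1 error rate (2-sided) by applying a Bonferroni correction for the three outcomes of interest". The overall rate being divided by three is 5%.
- **Table 2** gives 22, 95 and 50 per arm for knowledge, distress and depression, against 130 evaluable per arm expected at the time.
- **Amendment note of June 5, 2023:** the expected number completing visit 2 falls to 60 to 80 per arm. It adds: "With 60 to 80 per arm, we will still have adequate power for the knowledge and depression endpoints". Distress is not mentioned.

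No step-down, ordered or gatekeeping procedure is described for Aim 2.

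**The concern.** With 130 per arm expected and 95 needed for distress, the cost of single-step Bonferroni could be ignored. At 60 to 80 per arm it cannot: distress, one of three co-equal primary outcomes of Aim 2a, falls below the plan's own 85% target. The sample assumption was revised, but the multiplicity rule was not looked at again.

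Single-step Bonferroni holds each test to 1.67% whatever the other two show. Holm orders the three p-values and compares the smallest with 1.67%, the next with 2.5% and the largest with 5%, stopping at the first failure. It rejects everything Bonferroni rejects. The two rules differ most when some effects are much larger than others, which is the pattern in Table 2. Knowledge and depression will usually be rejected first, so distress will usually be tested at 5%. At stake is power that costs no patients and no loosening of the 5% error rate.

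**Working it through.** **Inputs (Table 2, change from baseline to post-testing, phone v. video).** Pooled SD = √((s₁² + s₂²)/2).

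| Outcome | Difference | Pooled SD | Standardised d |
|---|---|---|---|
| Knowledge | 18.6 − 5.7 = 12.9 | √((11.2² + 12.6²)/2) = 11.92 | 1.082 |
| Distress | 3.6 − (−2.6) = 6.2 | √((12.4² + 12.3²)/2) = 12.35 | 0.502 |
| Depression | −0.2 − (−1.6) = 1.4 | 2.0 | 0.700 |

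**Step 1: reproduce Table 2.** Two-sample t-test, noncentral t with 2n − 2 degrees of freedom and noncentrality d√(n/2), α = 0.05/3 two-sided, 85% power. The smallest n per arm is 22, 95 and 50, an exact match.

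**Step 2: distress power at the amended sample, by test level (same formula).**

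| n per arm | at 1.67% | at 2.5% | at 5% |
|---|---|---|---|
| 60 | 62.6% | 68.4% | 77.9% |
| 70 | 70.7% | 75.9% | 83.9% |
| 80 | 77.4% | 81.8% | 88.4% |

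The first column is Bonferroni. The last is the ceiling for Holm, approached when knowledge and depression are both rejected. At 1.67%, knowledge power is above 99.9% throughout, and depression power is 92% at 60 per arm and 98% at 80.

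**Step 3: Holm power by simulation.** Three t statistics at the effects above; ordered p-values against 0.05/3, 0.05/2 and 0.05; at least 200,000 trials per setting. The documents give no correlation between outcomes, so it was varied as an assumption (independent; 0.3; 0.5; up to 0.8 between distress and depression; −0.3 between knowledge and the other two).

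| n per arm | Distress, Bonferroni | Distress, Holm | Gain |
|---|---|---|---|
| 60 | 63% | 77% | about 14.5 to 15 points |
| 70 | 71% | 84% (83.4% to 83.7%) | about 13 points |
| 80 | 77% | 88% | about 11 points |

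Correlation moves the gain by less than half a point. Holm reaches 85% at 73 per arm; Bonferroni needs 95. The chance of claiming all three outcomes rises from 57–61% to 75–76% at 60 per arm, and from 76–77% to 88% at 80.

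**Step 4: how far the gain depends on the other two outcomes.** Distress effect held at 0.502, 60 to 80 per arm:

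| Other outcomes | Gain in distress power |
|---|---|
| Both as in Table 2 | 11 to 15 points |
| Depression effect halved | about 7 to 8 (extremes 6 to 9, by n and correlation) |
| Depression null | about 5 to 6 (6.0 at 60 per arm, 4.5 at 80) |
| Both null | about 0 (0.1 to 0.2) |

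The third row agrees with Step 2. When only knowledge is rejected first, distress is tested at 2.5%, and 68.4 − 62.6 = 5.8 points at 60 per arm.

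**Step 5: error control.** With m true nulls, at most 3 − m hypotheses can be correctly rejected before the first true null is reached, so its threshold is at most 0.05/m. The familywise error is therefore at most 5% under any correlation. In simulation it was at most 4.9% in every null configuration tried.

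**The case against.** **Bonferroni is valid.** It controls the familywise error at 5%, and choosing between two valid procedures can look like preference. This stands as far as calling it an error goes. A reader might infer that the plan's inference is faulty or its error rate uncontrolled; the documents do not support that.

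**The plan may not bind itself to 1.67% at analysis.** The figure occurs only in the sample-size paragraph, and sizing each test at 5%/3 is compatible with Holm at analysis. This stands. A reader might infer that every Aim 2a test is irrevocably held to 1.67%, but the analysis text does not say so. That silence is itself a reason to state the rule.

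**The gain is conditional and the remedy partial.** A reader might take 11 to 15 points as guaranteed, or conclude that Holm rescues distress. Neither follows: the gain shrinks as in Step 4, and at 60 per arm Holm power is 77%. The 60 to 80 are visit 2 completers, whereas the change score also needs the post-disclosure (T2) survey. At 50 evaluable per arm, Holm gives about 69%.

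**The pilot effects may not carry over.** The distress row is footnoted as the intrusive subscale, while section 3.3 specifies the 8-item scale. A rise of 18.6 in knowledge cannot be a raw one-point-per-item score on the 16-item knowledge scale, and the scoring is not given. This is a caution on Table 2 itself, and so on any power figure built on it.

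**Intervals.** Bonferroni has simple matching simultaneous confidence intervals and Holm does not. True, but the plan specifies none for these tests, and 98.33% intervals can still be reported.

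**Priority.** Section 4.0 calls the phone-versus-video comparison a secondary objective, and the note already limits its claim to knowledge and depression. Both are correct.

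**Conclusion.** The point holds as an efficiency improvement. At the Table 2 effects and 60 to 80 evaluable per arm in 1:1 allocation, replacing single-step Bonferroni with Holm raises distress power from about 63–77% to 77–88%, with the two-sided familywise error still at or below 5%. The 85% target then falls inside the expected range, at about 73 per arm, but is missed at its lower end.

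The size rests on the pilot effects for all three outcomes and on every visit 2 completer supplying a T2 score. It is nearly insensitive to the correlation between outcomes. That Holm does no worse than Bonferroni, and that it controls the error rate, rest on no such assumption. Aim 1, which decides whether the trial meets its primary objective, is unaffected.

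**What to change.** Before any Aim 2 data are compared by arm:

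1. Add to the Analyses for Aim 2 text, next to the sentence on t-tests: *The three Aim 2a primary hypotheses will be tested by Holm's step-down procedure at a two-sided familywise error of 5% (ordered p-values against 1.67%, 2.5% and 5%).*
2. Keep Table 2 at 1.67% and label it the conservative planning basis.
3. In the June 2023 note, state distress power at 60 to 80 per arm under this rule (about 77% to 88%), with its assumptions: Table 2 effects for all three outcomes, and evaluable rather than visit 2 completion numbers.
4. If simultaneous intervals are wanted, report 98.33% intervals and say that they are more conservative than the Holm decisions.

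The cost is a sentence of analysis text and an addition to the note, with no extra patients or data. The one loss is the simple match between intervals and tests. Made after arm-level results are known, the change would not be credible.

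### The Aim 2 power statement still rests on 130 per arm; at the amended 60 to 80 per arm, distress has at most about 63–77% power against the 85% target, and the subgroup statement goes beyond what Table 2 supports

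*Combined protocol and SAP*

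**What the plan says.** All of this is in section 4.0.

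- **Outcomes.** Under the Aim 2 analyses: "Our primary outcomes for Aim 2a include changes in 1) cancer related distress; 2) depression; and 3) knowledge". The Aim 1 sample size paragraph places the phone-versus-video comparison below the trial's primary objective: "comparison between the phone and videoconference groups (see Aim 2a) are secondary objectives".
- **Error rate and power.** "We assumed 85% power and a 1.67% Type I error rate", and "We used a 1.67% Type 1 error rate (2-sided) by applying a Bonferroni correction for the three outcomes of interest".
- **Expected size.** From 180 per arm randomised, with 28% lost, the plan expects about 130 evaluable per arm and concludes that "we have excellent power for all three arms with at least 95/arm, which is well below our expected 130/arm anticipated sample size". Table 2 compares two arms on three outcomes, so I read the three arms in that sentence as the three outcomes.
- **Subgroups.** "Table 2 also demonstrates that we have sufficient power for subgroup analyses, with a sample size of just 22/arm needed for knowledge comparisons".
- **Table 2, number needed per arm.** Knowledge 22, distress 95, depression 50.
- **June 2023 note, below Table 2.** "Our anticipated visit 2 completion sample size for the phone and videoconferencing arms will be 60 to 80 per arm", and then: "With 60 to 80 per arm, we will still have adequate power for the knowledge and depression endpoints". Distress is not mentioned.

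The footnote to the Schema says that the 60 to 80 already includes Arm C participants who receive services through the waitlist, so rerandomisation adds nobody further.

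**The concern.** The 130 per arm sentence and the June 2023 note both stand in the current text and give different sizes for the same comparison. The sentence is in the present tense and covers all three outcomes. The note covers two and gives neither power nor a detectable difference for the third. The whole amended range lies below the 95 per arm that Table 2 requires for distress.

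What is at stake is how a null distress result is read. A reader relying on 130 per arm would take it as strong evidence against the assumed difference, when the test has a materially larger chance of missing it than the plan accepted.

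The subgroup sentence is a smaller matter. It speaks of subgroup analyses in general but cites only the outcome with the largest assumed effect, and the note leaves it untouched. The Aim 2b analyses examine moderators of cognitive, affective and behavioural outcomes, so the wording bears on planned work.

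**Working it through.** **Inputs.** Two-sample t-test on change scores (Aim 2 analyses); two-sided alpha 0.05/3 = 0.0167; target power 85%; means and SDs from Table 2; equal arms.

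| Outcome | Difference | Pooled SD, √[(s₁²+s₂²)/2] | Standardised effect |
|---|---|---|---|
| Knowledge | 18.6 − 5.7 = 12.9 | √[(11.2²+12.6²)/2] = 11.92 | 1.08 |
| Distress | 3.6 − (−2.6) = 6.2 | √[(12.4²+12.3²)/2] = 12.35 | 0.502 |
| Depression | −0.2 − (−1.6) = 1.4 | 2.0 | 0.70 |

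**Formula.** With n per arm, the noncentrality is difference / (SD × √(2/n)) on 2n − 2 degrees of freedom. Power is the probability that this noncentral t exceeds the two-sided critical value.

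**Step 1: reproduce Table 2.** The smallest n per arm reaching 85% is 22 (knowledge), 95 (distress) and 50 (depression). All three match.

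**Step 2: power at the planned and amended sizes.** For distress at 60 per arm, the noncentrality is 6.2 / (12.35 × √(2/60)) = 2.75 against a critical value of 2.43. At 80 per arm it is 3.17 against 2.42.

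| n per arm | Distress | Depression | Knowledge |
|---|---|---|---|
| 60 | 62.6% | 91.8% | >99.9% |
| 80 | 77.4% | 97.7% | >99.9% |
| 95 | 85.1% | 99.2% | >99.9% |
| 130 | 94.9% | 99.9% | >99.9% |

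The chance of missing a true 6.2-point distress difference is therefore 37.4% at 60 and 22.6% at 80, against about 5% at 130 and the 15% accepted in the plan.

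**Step 3: detectable distress difference at 85% power.** Solving the same formula for the difference gives 7.83 points at 60 per arm and 6.76 at 80, against 6.2 assumed.

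**Step 4: why these are upper limits.** The 60 to 80 counts visit 2 completers. The change score needs a usable T2 survey, and the footnote to Table 1 allows late surveys (7 to 14 days) to be dropped and imputed. If some surveys are missing or dropped, n falls below 60 to 80.

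**Step 5: subgroups, from Table 2's own sizes.** For both sides of a two-way split to reach the tabled size, an arm needs:

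- knowledge: 2 × 22 = 44
- depression: 2 × 50 = 100
- distress: 2 × 95 = 190

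At 60 to 80 per arm only knowledge can satisfy this, and then only if the smaller subgroup holds at least 22/60 = 37% or 22/80 = 28% of the arm. For depression, one subgroup can reach 50 if it holds 50/60 = 83% or 50/80 = 62.5% of the arm, but two cannot. Distress needs 95, more than the whole arm.

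These are sizes for a comparison within a subgroup. The Aim 2b moderator models test arm, time and moderator interactions, which Table 2 does not address.

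**The case against.** The strongest reply is that the section already deals with this. The note is dated, sits below Table 2, gives the new size, describes the earlier number as an initial goal, and confines its claim to knowledge and depression. With 95 per arm shown for distress just above it, a careful reader can work out the shortfall. Keeping the old rationale and adding a dated note is a legitimate audit trail, and the condition of at least 95 per arm remains true as a condition.

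Most of that stands. A reader might infer that the plan hides a loss of power; the note does not support that, because it gives the new size and leaves distress out of its reassurance. What remains is that the 130 per arm sentence is not marked as superseded and that no figure is given for distress. The note also sets 60 to 80 completers against 180 randomised, when the like-for-like planned figure is 130 evaluable.

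On subgroups, the reply is that the sentence names knowledge as its basis, that the plan sets no 85% standard for subgroups, and that doubled t-test sizes do not measure power for interaction models. This also stands in part. A reader might infer that the amendment broke the subgroup claim for every outcome but knowledge. The figures do not support that: a two-way split for distress needs 190 per arm and already failed at 130, and depression can still reach its tabled size in one large subgroup. The valid point is narrower: the general wording goes further than the one figure cited.

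**Conclusion.** The concern holds in limited form. The standing sentence claims excellent power for all three outcomes at a size the plan no longer expects. At 60 to 80 per arm, distress power is at most about 63–77% against 85%. The note concedes this only by omission.

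The result assumes Table 2's differences and SDs, equal arms, a two-sided 1.67% level and a usable T2 survey from every visit 2 completer; if that last assumption fails, power is lower.

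It should not be read as an error in Table 2, which reproduces exactly, or as a weakness of the whole trial. Overall knowledge and depression stay above 85% under Table 2's assumptions, and Aim 1 is untouched. The affected outcome is one of three in a comparison that the plan itself ranks as a secondary objective. Correction is worthwhile because it governs how a null distress finding will be interpreted.

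**What to change.** 1. Mark the 130 per arm sentence as the original plan, superseded by the 60 to 80 per arm of June 2023, and write outcomes where it says arms. The original rationale can stay on record.
2. Add to the note that distress power at 60 to 80 per arm is at most about 63–77%, below the 85% target (or that the difference detectable with 85% power is about 7.8 to 6.8 points against 6.2 assumed), that missing or dropped T2 surveys reduce it further, and that a null distress result is to be read accordingly.
3. Narrow the subgroup sentence. Table 2 supports phone-versus-video comparisons only in subgroups that reach the tabled size: 22 per arm for knowledge; 50 per arm for depression, which at most one large subgroup can reach; none for distress. State that it does not establish power for the Aim 2b interaction tests.

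The cost is text only: no new participants and no change to tests, alpha or conduct. The stated power becomes less favourable, with distress openly below target and a smaller subgroup claim.
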